Considerable effort has now been invested in making better accelerometers and validating them against DLW. In preparation for this grant we conducted a comprehensive review of the published literature (see Appendix A, Table 1). The current generation of triaxial accelerometers is now sensitive, robust and easy to use. Based on 4 separate studies (total n = 91), the weighted correlation between kcal/day from the accelerometer and DLW was 0.62 (see Appendix A, Table 2) [57-60]. On-going methodological work (cf D.4.1.1) should further improve precision and make it feasible to move this research forward rapidly.

Data on energy intake (EI), and as well as macronutrient composition (eg, % of calories from fat, carbohydrate and protein) are also important for assessing energy balance. Measurement of intake in free-living people can be difficult, however [61-67]. Food frequency questionnaires (FFQ) are known to have important limitations, both in estimation of total calories and composition [68]. Furthermore, no single FFQ would be appropriate for our heterogeneous populations. Multiple twenty-four hour recalls are therefore the best option for international comparisons, even though they are labor-intensive [69-72]. Energy adjustment will also improve estimation of composition [68, 73]. Likewise, intake of manufactured foods, soda, etc, which are measured with less error may be key aspects of an obesogenic environment, especially in the context of rapidly modernizing societies.

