**Table 1. Participant Characteristics by Site – mean (SD)**

	Jamaica	Maywood	Nigeria	Seychelles	S. Africa
n (M/F)	41 (18/23)	36 (16/20)	38 (20/18)	45 (22/23)	38 (16/22)
Age (yrs)	37.9 (8.6)	38.3 ± 10.1	38.9 ± 13.2	35.2 ± 5.7	27.2 ± 5.0
BMI					
males	23.6 (3.5)	27.3 ± 6.5	22.5 ± 2.9	26.6 ± 3.3	21.8 ± 2.0
females	30.6 (5.3)	33.7 ± 9.4	26.2 ± 6.4	26.9 ± 6.4	29.8 ± 7.3
Activity Counts					
males (cts/d)	364040 (158584)	313988 ± 217868	241191 ± 103401	275078 ± 130813	379480 ± 159859
females	209277 (94637)	280929 ± 175078	181312 ± 105667	170670 ± 76242	293548 ± 182584
AEE (kcal/d)					
males	1050 (306)	1090 ± 387	688 ± 253	902 ± 254	911 ± 329
females	884 (306)	1090 ± 566	608 ± 230	617 ± 292	1000 ± 514
AEE/kg (kcal/kg/d)					
males	15.06 (3.76)	13.25 ± 5.71	10.45 ± 3.83	11.45 ± 3.08	14.37 ± 5.35
females	11.13 (3.75)	12.42 ± 5.66	9.14 ± 3.88	8.73 ± 3.16	13.29 ± 6.06
AEE adj. for wt					
males (kcal/d)	1094 (271)	985 ± 426	761 ± 262	866 ± 239	1011 ± 319
females	838 (287)	970 ± 532	660 ± 220	667 ± 227	999 ± 467
Pop. Mean BMI*					
males	23.7 (4.5)	26.7 (5.5)	22.6 (4.5)	25.1 (4.4)	22.9 (6.0)
females	28.0 (6.4)	29.8 (8.1)	22.9 (6.0)	27.6 (6.3)	27.1 (9.1)

\* Population mean BMI for 25-45 year olds based on representative sampling

The absolute activity EE levels are supported by data on the % of time spent in sedentary vs. moderate activity, with Jamaican and South African males, who were primarily laborers, spending less time in sedentary activity than Nigerian or Seychelles women, as recorded by the accelerometer (Table 2). There was an inverse association between activity counts and BMI (Figure 4) indicating a cross-sectional relationship between adiposity and PA. We acknowledge that heterogeneity exists by gender, but caution against interpretation of sub-groups given the small sample size.

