#### D.4.1.1 Physical Activity by Accelerometer

PA will be measured using the Actical activity monitor (Respironics/Mini-Mitter, Bend, OR) with all participants. Previous studies have shown that accelerometer-based activity monitors can discriminate differing intensities of activity [151-156], making it possible to adequately characterize each of the study communities with regard to overall intensity of PA. We will record the data as activity counts/min and kcal/d. The activity monitor records the intensity, duration and frequency of physical motion through the use of an accelerometer which produces a variable electrical current based on the combination of the amplitude and frequency of motion. Accelerometers are omnidirectional motion sensors that count the vertical and horizontal acceleration of the user. This information is stored within the instrument as activity counts per epoch, or specified subunit of time, e.g., per minute. As the intensity of the activity increases, so does the number of activity counts per epoch. The Actical monitor is lightweight, waterproof and made to be worn on the wrist, waist or ankle. Consistent placement of the activity monitor ensures comparability of data. For this study, the monitor will be worn at the waist. There are concerns about the ability of the accelerometer to discriminate between some activities with differing energy expenditures, eg, stair climbing versus level walking. As described below, our consultants are developing methods to improve accuracy of these instruments.

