#### **D.7.1.1 Weight and Body Composition are Related to AEE at Baseline**

##### **D.7.1.1.1 AEE, Weight and Body Composition**

Two measures of AEE will be available. At baseline, we will have 500 participants/site with data from the accelerometer, inclusive of those who have both DLW and accelerometer (total N, all sites = 2500; 6 days

of monitoring). We will have data generated by DLW for 75 participants/site (total N, all sites = 375). The structure of the analysis will be similar with both exposure measures.

We anticipate that data for all the primary outcomes will not conform entirely to a normal Gaussian distribution. Using BMI, PAL and AEE data collected in previous studies in Maywood (n = 567) and Nigeria (n = 735), we examined the probability distributions. A formal test statistic was performed that combines kurtosis and skewness [180] as implemented in STATA with p-values less than 0.001, suggesting deviations from normality. Kernel density estimates of the BMI, AEE, and PAL distributions are depicted in Figure 7. After applying the ladder of power approach suggested by Tukey [181], we found that BMI, AEE and PAL for both sites appear to deviate from normality. Although no transformation is preferred after application of the ladder of powers method, two potential transformations are suggested by this approach, namely  $\log X$  and  $X^{-1}$ . Tukey's approach followed by formal testing will be carried out once data on all subjects in the study has been collected and a decision about data transformations has been made. Despite the lack of normality exhibited and corroborated by the statistical tests performed, a visual exploration of Figure 7 suggests only slight deviations from normality, mostly due to well-known skewness of these distributions. Thus, we anticipate the statistical methods that make use of normally distributed data will be appropriate to analyze these data. Of course, the degree of appropriateness of these methods will depend on their robustness to deviations from normality. If it is necessary, appropriate transformations will be carried out before statistical tests are performed.

**Figure 7.** Distribution estimates of main analysis variables BMI, AEE, and PAL in two sites: Maywood (US) and Nigeria.

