Following transformation of the appropriate exposure and outcome variables, Fisher's Z-transformation test will be applied in order to test hypotheses involving correlations. The resulting parametric test will be more powerful than other distribution-free approaches. The results will be corroborated by applying Spearman rank correlations and another parametric test based on the concordance coefficient introduced by Lin [182] and later extended by Chinchilli and colleagues to include repeated measures [183]. Lin's concordance correlation allows the comparison of the correlations accounting for possible differences in the mean values of the two variables under consideration. Furthermore, approximate permutation tests [184, 185] will be implemented using each of the three statistics: Pearson, Spearman and Lin's concordance, to compare agreement of the association between AEE and BMI across the three groups under investigation.

Correlation coefficients will be estimated using the Pearson correlation and confidence intervals constructed after applying the Fisher's Z-transformation. Furthermore, computer intensive statistical methods, such as bootstrapping, will be used to construct confidence intervals for both parametric and nonparametric approaches. Comparisons of these correlations will be carried out using this statistic for 1 and 2 samples [186], as well as approximate permutation tests [184, 185]. In addition, multivariate regression analysis will be fit to adjust for potential confounders. Confounders will include age, gender, and any other significant

predictors defined by the univariate analyses. Potential non-linear functions will be explored to see if they fit the data better. Sub-group analyses will be undertaken, with participants in each site divided by gender.

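### Lin's concordance coefficient is planned for AEE against BMI, which share no scale, so it can differ between sites whose correlations are identical

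*Combined protocol and SAP*

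**What the plan says.** Section D.7.1.1.1 names Fisher's Z as the lead test for correlations. It then plans to corroborate the results with Spearman's rank correlation and "another parametric test based on the concordance coefficient introduced by Lin". The reason given is that Lin's coefficient compares correlations while "accounting for possible differences in the mean values of the two variables under consideration". The same paragraph uses Pearson, Spearman and Lin as statistics in approximate permutation tests "to compare agreement of the association between AEE and BMI across the three groups under investigation". The next paragraph adds that "bootstrapping, will be used to construct confidence intervals for both parametric and nonparametric approaches".

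For the scale of the variables, D.4.1.1 says of the accelerometer: "We will record the data as activity counts/min and kcal/d". In D.7.1.1.1, "two potential transformations are suggested by this approach, namely" the logarithm and the reciprocal, with the choice left until the data are in. Nothing in the document places AEE and BMI on one scale.

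**The concern.** Lin's coefficient asks whether two measurements give the same number. It penalises any gap between the two means and any difference between the two SDs. That is useful when both measure one quantity in one unit. For an energy expenditure and a body mass index, the gap between means has no meaning and changes whenever the unit of AEE changes. What the plan presents as an advantage is therefore the defect.

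The exposed step is the comparison across groups. Sites differ in mean AEE, mean BMI and both SDs; the study was designed for that contrast. Lin's coefficient turns these differences into apparent differences in association. A corroborating test could then contradict Fisher's Z for reasons unrelated to how AEE and BMI relate. Section D.7.1.1.2 recognises that unequal SDs can distort standardised regression coefficients across sites, but D.7.1.1.1 gives no such caution for Lin's coefficient.

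**Working it through.** **The plan's own figures.** The plan gives no number for Lin's coefficient. The nearest figures are the D.7.2 powers for comparing two correlations with 150 people on each side, one-sided. With z = |atanh r₁ - atanh r₂| / √(2/147) and power = Φ(z - 1.645), the results are 91.5% (-0.4 v -0.65; plan: over 91%), 80.1% (-0.45 v -0.65; plan: over 80%) and 87.8% (-0.35 v -0.6; plan: over 85%). They reproduce, and they do not involve Lin's coefficient.

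**Formula.** CCC = 2·r·s₁·s₂ / (s₁² + s₂² + (m₁ - m₂)²), with m and s the mean and SD of AEE (1) and BMI (2).

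**Inputs.** Means and SDs by site and sex are from Table 1, with 16-23 people per cell. Counts/min is Table 1 counts/d divided by 1440. r = -0.5 at every site is one end of the D.7.2 range for DLW activity and body composition, borrowed for BMI.

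**Two cells in full (men, kcal/d).**
- Maywood: AEE 1090 (387), BMI 27.3 (6.5). CCC = -2515.5 / (149,769 + 42.25 + 1,129,331.29) = -0.0020.
- South Africa: AEE 911 (329), BMI 21.8 (2.0). CCC = -658 / (108,241 + 4 + 790,676.64) = -0.0007.

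The same correlation gives coefficients 2.7-fold apart. The squared gap between means dominates the denominator.

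**All sites, r = -0.5.**

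| AEE scale | Men: range (ratio) | Women: range (ratio) |
|---|---|---|
| kcal/d | -0.0007 to -0.0020 (2.7) | -0.0020 to -0.0043 (2.2) |
| counts/min | -0.0031 to -0.0166 (5.3) | -0.020 to -0.031 (1.5) |
| log, AEE in kcal/d | ratio 2.5 | ratio 2.2 |
| 1/X, AEE in kcal/d | ratio 2.4 | ratio 2.5 |

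The last two rows transform both variables and assume log-normality. Neither transformation removes the site differences. Moving from kcal/d to counts/min also exchanges Nigeria and Seychelles in the site order in both sexes, though they are close in counts/min (men -0.0080 v -0.0085; women -0.0306 v -0.0302).

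**Within one site.** Permuting BMI against AEE leaves all means and SDs unchanged. CCC is then a fixed multiple of r, so its p-value equals Pearson's. It is redundant there.

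**Between sites.** Bivariate normal data in kcal/d were simulated with the same r in both sites, for the 20 same-sex site pairs, at nominal 5%. Cell sizes are 75 and 500 per site (D.7.1.1.1), halved by sex (D.3.2): about 37 and 250. For the accelerometer, B.5 reports that "the weighted correlation between kcal/day from the accelerometer and DLW was 0.62". Assuming simple attenuation, 0.62 × -0.5 = -0.31 and 0.62 × -0.6 = -0.37. Raw site labels were permuted (299 permutations; 1,500 replicates at 37, 1,000 at 250; Monte Carlo SE about 0.6-0.7 points at 5%).

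| Sample | r | Lin, false rejection over pairs | Pairs above 50% |
|---|---|---|---|
| 37 per sex | -0.5 | 1-35% (8 pairs above 10%) | 0 |
| 37 per sex | -0.6 | 1-44% | not tallied |
| 250 per sex | -0.2 (assumed) | 1-36% | 0 |
| 250 per sex | -0.31 | 1-71% | 5 |
| 250 per sex | -0.37 | 2-82% | 6 |

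Pearson's r rejected in 1-7% (37 per sex) and 2-7% (250 per sex).

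A 95% percentile-bootstrap interval for the between-site difference (499 resamples per site, 1,000 replicates) excluded zero for Lin in 7-39% (37 per sex, r = -0.5) and 6-83% (250 per sex, r = -0.31), against 4-8% for Pearson. The problem is not confined to one resampling scheme.

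**The case against.** The strongest reply concerns weight. Lin's coefficient only corroborates. Within a site it is harmless, and D.7.2 says the study is not powered to compare associations across sites. The coefficients are so near zero that a reader who sees -0.001 beside r = -0.5 would probably suspect a scale artefact. This stands and limits the severity.

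The simulation figures also rest on stacked assumptions: a permutation scheme the plan does not state, site pairs rather than three groups, correlations borrowed from body composition, a 0.62 that may describe total rather than activity energy expenditure, and pilot cells for which the protocol itself gives a "caution against interpretation of sub-groups given the small sample size". The ranges stress the extremes. In a smaller run (300 replicates, 199 permutations) the median false rejection over the 20 pairs was about 9% (37 per sex, r = -0.5), 16% (250 per sex, r = -0.31) and 9% (250 per sex, r = -0.2). At r = -0.1 with 250 per sex it was about 5%, with a maximum of 16%. The percentages are therefore illustrations, not forecasts. The change in site order is mostly an exchange of near-ties and carries little weight.

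One could also hope that the re-scaling allowed in D.7.1 and D.7.1.1.1 would help. Those passages concern the shape of distributions, and none specifies standardisation within site. Nor can the text be read as meaning accelerometer against DLW, since it names AEE and BMI.

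**Conclusion.** The concern holds. Lin's coefficient is the wrong statistic for AEE against BMI. The algebra alone shows that equal correlations generally give unequal coefficients when means or SDs differ, and that the result depends on the unit of AEE. The size, 1.5- to 5.3-fold between sites on the two recorded scales, rests on the small Table 1 cells and an assumed common correlation. The false-rejection rates further assume normality and a resampling scheme.

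The effect on the study is minor to moderate. The Fisher's Z analysis, hypothesis 1 on percent body fat, the slope-by-site test in D.7.1.3 and the pooling of sites in D.7.2 are unaffected. What is at risk is a spurious finding of heterogeneity, or a spurious failure to corroborate. Separately, the three groups are not defined in this five-site study and no permutation scheme is given, so the comparison cannot be run as written.

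**What to change.** In D.7.1.1.1:

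- Remove Lin's coefficient from the AEE-BMI association and its comparison across groups. Keep Pearson with Fisher's Z, Spearman, and the slope-by-site interaction test of D.7.1.3. Nothing is lost: with both variables standardised within site, Lin's coefficient equals Pearson's r.
- Define the three groups and state what is permuted. If site labels are permuted, first standardise both variables within each site. Pearson's false rejection over the 20 pairs is then 3.7-5.0% at 37 per sex and 4.2-5.6% at 250 per sex. This is a modest gain on the raw-label rates.
- Assign Lin's coefficient to the accelerometer-DLW comparison already planned in D.4.1.1 and listed under concordance in Table 5, where both readings are in kcal/d.

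The cost is SAP wording only, with no change to data collection or sample size.

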#### D.3.2 Sampling Procedures

In each of the 5 sites, 75 individuals aged 25-45 years will be recruited for the DLW protocol and 425 will be recruited for the accelerometer protocol, with equal numbers of men and women. We will exclude individuals with obvious chronic or infectious diseases (including active malaria), pregnant or lactating women, and HIV positive individuals (see D.3.3 for HIV testing procedures). Any individual that has a condition preventing normal AEE will also be excluded from our study. Population-based surveys have been carried out in each of the sites; the sampling procedures used previously will be employed in the present study. These study sites were chosen because mean BMIs and prevalence of obesity span the healthy physiological range.

Jamaica – Spanish Town is an urban area 25 km from the center of Kingston. Once the capital of colonial Jamaica, Spanish Town is an established community with a population of 92,000 in 1991; about 45,000 individuals are between the ages of 25 and 74. A community-based study of hypertension and diabetes (n=3500) has been completed [123]. Districts were randomly sampled; beginning from a fixed point in each district (e.g., the north-west corner), door-to-door screening took place. Examinations will be carried out in the local health clinic and specimens taken immediately to the Univ. of the West Indies for processing.

US – Maywood is an African-American working class community adjacent to the western border of Chicago, Illinois. Approximately 3,500 participants have been examined in our clinic since 1991 for both observational and interventional studies [123]. Participation rates for observational components of these studies have been 60% or greater. Project staff are residents of the community and conduct all recruitment and home visits. We have now contacted individuals on approximately two thirds of the blocks in Maywood and are well known to the community. The Department clinic is on campus, within walking distance of most neighborhoods and is well known to local residents. We will also recruit from the adjoining west side of Chicago.

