### **D.7.1 Statistical Analysis**

In the initial stage of the analysis, a complete set of descriptive tables will be produced by gender within site. The distributional properties of each variable will be examined and appropriate re-scaling undertaken, if necessary. All outliers (i.e.  $> 3$  SD's) will be identified and either verified as correct or set to missing. When possible, internal validity will be assessed by the use of bivariate scatter plots of variables known to be correlated (e.g., resting EE vs. BMI or weight vs. BP). These plots provide a useful search procedure for unanticipated outliers and/or non-linear relationships.

As in any other longitudinal study, some measurements may be unavailable in a subset of the study participants. A brief description of methods used to handle non-ignorable missing data are presented at the end of this section (cf. D.7.4)

*We describe below the analytic procedures and the power calculation, in relation to the following 4 primary hypotheses as stated in the Aims:*

- 1) AEE is negatively related to % body fat at baseline, independent of dietary intake.
- 2) AEE is negatively related to change in body weight during follow-up, independent of dietary intake.
- 3) Mean levels of AEE are negatively related to mean levels of obesity/relative weight among the populations.
- 4) Adipocytokines and hormones influence weight regulation and insulin sensitivity and interact with AEE.

[figure not shown]

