#### *D.7.1.2 AEE and Weight Change*

The study design contemplates 3 weight determinations over time: one at baseline, a second after 12 months, and a final assessment 2 years after entering the study. To better understand the associations between AEE and body composition, the analysis plan will be carried out in incremental steps corresponding to the degree of sophistication of the statistical methods used.

- 1) Descriptive: Weight change is computed for each subject as the subject's last weight minus baseline weight. The correlation between weight change and AEE will be computed.
- 2) Regression of weight change (as computed above) on AEE will be performed, adjusting for potential confounders of the association.
- 3) AEE will be dichotomized at the median value, resulting in high and low AEE groups. Weight change will be estimated for each individual as the slope of the regression of weight on time (0, 12, and 24 months). Average weight change across AEE groups will be compared. That is, individual regression lines of weight on time will be obtained for each individual, and the average regression among "Low PA" will be compared to the average regression among "High PA" subjects.
- 4) Multilevel analysis (i.e., mixed effect models), which generalizes the previous methods, will be used in our final analysis. This approach will allow for the use of all the available information (i.e., there will be no need to categorize AEE values), thus improving the statistical power [189]. Furthermore, this method allows one to account for the within-subject correlation of the weight determinations and to account (adjust for) subject-specific covariates that may confound the associations. In addition, the dependence of weight change on AEE values can be specifically modeled by the use of random coefficients. Specifically,

$$\text{Level 1: } W_{ij} = \beta_{0i} + \beta_{1i} T_{ij} + \varepsilon_{ij}$$

$$\text{Level 2: } \beta_{0i} = \gamma_0 + \gamma_1 AEE_i + \Omega X_i + \xi_{0i}$$

$$\beta_{1i} = \alpha_0 + \alpha_1 AEE_i + \Psi Z_i + \xi_{1i}$$

$$\varepsilon_{ij} \approx N(0, \sigma^2); \xi_{0i} \approx N(0, \delta_0^2); \xi_{1i} \approx N(0, \delta_1^2); \text{corr}(\xi_{0i}, \xi_{1i}) = \delta_{01}$$

$$\text{corr}(\varepsilon_{ij}, \xi_{0i}) = \text{corr}(\varepsilon_{ij}, \xi_{1i}) = 0$$

$$i = 1, \dots, n; \quad j = 0, 1, 3$$

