## D.7.2 Power Analysis

A statistical justification for the selected sample size is provided for each aim of the study according to the suggested analytical plan. Sample size estimation for each of these hypotheses will be obtained, and the maximum number required to test them with sufficient power (80% or higher) will be selected.

- 1) PA is negatively related to percent body fat and CV risk factors in the study populations at baseline.

It has been previously estimated (cf. Preliminary Studies) that the correlation between PA, measured with DLW, and body composition is between -0.6 and -0.5. A correlation of -0.33 or smaller (larger in absolute value) will be detectable with 83% power and maximum probability of type I error alpha = 5% using a one-sided Fisher's Z test and 75 subjects per site [194].

- 2) PA is negatively related to change in body fat composition.

- a) *Physical Activity Measured by Accelerometer:*

PA, measured by the accelerometer, is associated with changes in body composition. For design purposes we will use the approach described above in the analysis section (see D.7.1.2. method 3). That is, two AEE groups will be formed by using the median AEE as the cut point. A method developed by Frison and Pocock [195] will be applied to compare mean changes between groups in a longitudinal analysis, adjusting for baseline values. In this method the following assumptions are made: the correlation between any 2 weight determinations is ~ 0.60 and the minimum acceptable difference between the means is 0.25 standard deviations (i.e., effect size equals 0.25) [186]. There will be one baseline measure of weight and two follow-up measurements. An analysis of covariance approach will be used to adjust for baseline values. Thus, to detect the pre-specified minimum difference with 90% statistical power we will need to accrue 460 subjects per AEE group (230 in the Low and 230 in the High group). We will accrue a total of 500 individuals per site in anticipation of a conservative total attrition rate of ~ 20%.

- b) *Physical Activity Measured by Doubly Labeled Water:*

The correlation between AEE and change in body composition is anticipated to be weaker (i.e., smaller in absolute value) than that observed between AEE and body composition at baseline. Data from previous studies (cf. Section C: Preliminary Studies) suggest that the association between AEE and body composition remains constant across studies.

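### The correlation test for Hypothesis 1, its power and the cross-site comparisons are not adjusted for sex, and the plan does not say whether the crude or the adjusted result decides the hypothesis.

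*Combined protocol and SAP*

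**What the plan says.** Hypothesis 1 in D.7.1 is that "AEE is negatively related to % body fat at baseline, independent of dietary intake". D.7.1.1.1 states that "Fisher's Z-transformation test will be applied in order to test hypotheses involving correlations". On estimation it says "Correlation coefficients will be estimated using the Pearson correlation and confidence intervals constructed after applying the" Fisher transformation, and it compares the AEE-BMI association across groups with the same kind of statistic. A multivariable regression is then added, with age, gender and whatever else is significant univariately as confounders. Sub-group analyses by gender within site follow, and the section later says that all analyses will use multivariable linear regression. It does not rank these results. It also leaves the scale of AEE open: Table 1 alone shows counts, kcal/d, kcal/kg/d and weight-adjusted kcal/d.

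D.7.2 item 1 powers the hypothesis on one correlation per site: "A correlation of -0.33 or smaller (larger in absolute value) will be detectable with 83% power", with "maximum probability of type I error alpha = 5% using a one-sided Fisher's Z test and 75 subjects per site". Item 2b compares correlations between groups of sites. Neither item mentions sex. D.3.2 recruits each site "with equal numbers of men and women".

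**The concern.** If men are more active and leaner than women, a sample that mixes the sexes can show a negative AEE-fatness correlation even when the two are unrelated among men and among women. That is the direction Hypothesis 1 predicts, so the error favours the hypothesis.

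Three things are at stake.

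- A crude correlation could be declared significant while the gender-adjusted slope is null, and the plan gives no rule for reading that result.
- Sites could appear to differ in correlation only because their sex gaps differ.
- A crude correlation cannot support the part of the hypothesis about independence from diet. In D.7.1.1.1, dietary intake enters the regression only if it turns out to be a significant univariate predictor.

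**Working it through.** **1. The plan's own power figure.** Fisher's Z power is Phi(atanh|r| × sqrt(n-3) - z). For r = 0.33 and n = 75, atanh(0.33) = 0.3428, sqrt(72) = 8.485 and the product is 2.909.

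- One-sided 5%: Phi(2.909 - 1.645) = 89.7%.
- Two-sided 5%: Phi(2.909 - 1.960) = 82.9%.

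The stated 83% therefore fits a two-sided test, not the one-sided test the text names. The smallest significant |r| at n = 75 is tanh(1.645/8.485) = 0.19 one-sided and tanh(1.960/8.485) = 0.23 two-sided.

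**2. Correlation produced by sex alone.** Assume a 1:1 sex mix and no association within either sex. Then r = r(sex, activity) × r(sex, fatness). Each factor is 0.5d / sqrt(s² + d²/4), where d is the male-minus-female difference in means and s² is the average of the two within-sex variances. All means and SDs come from Table 1.

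Jamaica, counts with pilot BMI:

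- Counts: d = 364040 - 209277 = 154763; s = 130585; factor = 77382 / 151791 = 0.510.
- Pilot BMI: d = 23.6 - 30.6 = -7.0; s = 4.49; factor = -3.5 / 5.694 = -0.615.
- Product: 0.510 × -0.615 = -0.313.

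Jamaica with the population BMI row: d = 23.7 - 28.0 = -4.3; s = 5.53; factor = -2.15 / 5.935 = -0.362; product -0.185.

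The same steps for every site:

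| | Jamaica | Maywood | Nigeria | Seychelles | S. Africa |
|---|---|---|---|---|---|
| Counts, pilot BMI | -0.313 | -0.031 | -0.096 | -0.013 | -0.145 |
| Counts, population BMI | -0.185 | -0.018 | -0.008 | -0.098 | -0.064 |
| AEE/kg, pilot BMI | -0.285 | -0.027 | -0.058 | -0.012 | -0.056 |
| Unscaled kcal/d, pilot BMI | -0.161 | 0.000 | -0.057 | -0.014 | +0.061 |

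**3. Rejection rate of the one-sided 5% test at n = 75.** This is Phi(atanh|r| × 8.485 - 1.645) for a negative r. The nominal rate is 5%.

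| | Jamaica | Maywood | Nigeria | Seychelles | S. Africa |
|---|---|---|---|---|---|
| Counts, pilot BMI | 87% | 8% | 20% | 6% | 34% |
| Counts, population BMI | 48% | 7% | 6% | 21% | 14% |

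**4. Percent body fat, the outcome named in Hypothesis 1.** Table 3 gives it for women only, so the sex gap is an assumption: 8 to 15 points, with within-sex SD 7 to 8.8. The factor for fat then runs from -0.41 (gap 8, SD 8.8) to -0.73 (gap 15, SD 7). Multiplied by the AEE/kg factors, 0.464 in Jamaica and 0.400 in Seychelles, this gives:

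- Jamaica: -0.19 to -0.34, rejection 50-91%.
- Seychelles: -0.17 to -0.29, rejection 41-82%.
- Maywood and South Africa: -0.03 to -0.07, rejection 8-14%.

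**5. Cross-site comparison.** On counts with pilot BMI, Jamaica and Seychelles would differ by 0.30 through sex alone (-0.313 against -0.013). With population BMI, the widest difference is 0.18 (Jamaica -0.185 against Nigeria -0.008). The illustrative differences in D.7.2 item 2b are 0.20 to 0.25.

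**6. Cost of adjusting.** With q covariates, n-3 becomes n-3-q. At r = -0.33 and n = 75:

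| q | One-sided | Two-sided |
|---|---|---|
| 0 | 89.7% | 82.9% |
| 2 (sex, age) | 88.9% | 81.8% |
| 5 (three dietary terms added, assumed) | 87.7% | 80.1% |

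**The case against.** The best defence is that the plan already handles sex. D.7.1.1.1 lists gender as a confounder in the regression and divides each site by gender. D.7.1 produces descriptive tables by gender within site, and Table 5 lists dietary intake as a covariate. This stands as far as it goes: the adjusted analysis will exist, so a reader should not infer that sex is ignored. It does not settle which result carries Hypothesis 1, and the power and the comparisons of correlations remain on the crude statistic.

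The size is also open to challenge, and much of that challenge is right. The largest BMI-based value comes from one site, with activity counts and pilot cells of 16 to 23 people per sex. The population BMI rows weaken it to -0.185. Unscaled kcal/d gives nothing in Maywood and the opposite sign in South Africa. The pilot data are accelerometer values, whereas the 75 per site are the doubly labeled water subset.

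Two stronger readings are tempting, and the documents do not support them.

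- A reader might infer that the study is sized on -0.33 and that sex alone nearly reaches it. In D.7.2 that value is only what the 75-per-site subset can detect, against an anticipated range in which "the correlation between PA, measured with DLW, and body composition is between -0.6 and -0.5". The 500 per site comes from the weight-change calculation.
- A reader might infer that Hypothesis 2 fails in the same way, because in method 3 of D.7.1.2 "AEE will be dichotomized at the median value, resulting in high and low AEE groups". That is an intermediate step. The stated final analysis there is a mixed model with continuous AEE, and its confounders include demographic and energy-intake variables. Nothing in the documents shows that sex predicts weight change.

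**Conclusion.** The concern holds in a limited form. The correlation test for Hypothesis 1, its power and the cross-site comparisons use a statistic that sex can confound in the hypothesised direction, and the plan does not name the adjusted result as decisive. On activity counts and BMI, sex alone could raise the one-sided rejection rate at n = 75 from 5% to about 48-87% in Jamaica and to 6-34% elsewhere. For percent body fat, Seychelles joins Jamaica, but only under the assumed sex gap.

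These figures rest on the Table 1 pilot means and SDs, an exact 1:1 sex mix, no within-sex association, and accelerometer measures standing in for doubly labeled water. They show what the crude test could do at some sites and on some scales. They do not show that a negative correlation at any site would be spurious.

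**What to change.** In D.7.1.1.1, name as the decisive test of Hypothesis 1 the partial correlation of AEE with percent body fat, or the equivalent regression coefficient. Adjust it for sex, age and a stated set of dietary-intake covariates, and use Fisher's Z with n-3-q. State the AEE scale. Keep the crude correlation as descriptive only.

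Use sex-adjusted correlations wherever sites are compared, in D.7.1.1.1 and in D.7.2. Restate the D.7.2 power for correlations on that basis, and make the sidedness of item 1 agree with its 83%.

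The change is to wording only and uses data already planned. At n = 75 and r = -0.33, adjusting for sex and age costs about 1 point of power, and five covariates in all cost about 2 to 3 points. At 500 per site the lost degrees of freedom are negligible.
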